2.1.2.3 Multiple assessments within visit windows

It is possible that multiple assessments of a patient fall into the same visit-window (e.g. due to unscheduled visits). All results (scheduled and unscheduled) will be displayed in listings, but only one value (observed or derived) will be selected for summary statistics by visit-window.

For **quantitative variables**, the assessment closest to the target day will be selected. If more than one assessment is at the same distance to the target day, the later one will be selected. For tables displaying the worst case scenario, such as shift tables or notable abnormalities, all assessments within a visit window will be used to identify the worst (e.g. the maximum or the minimum depending on parameter). Where applicable it will be defined for each parameter what the worst case is.

For **qualitative variables**, the worst record is selected; it is noted that in the relevant data subsection, worst case is always well defined.

2.2 Analysis sets

All screened patients (SCR): The SCR set comprises all patients who were screened.

Full analysis set (FAS): The FAS comprises all randomized patients with assigned treatments. Patients will be analyzed according to the randomized treatment assignment following the intention-to-treat (ITT) principle, even if they actually received no or a different treatment.

The FAS will be used for the summary of demography and baseline characteristics as well as for all efficacy analyses.

Per-protocol set (PPS): The PPS is a subset of FAS, consists of all randomized patients who take at least one dose of study medication and have no major protocol deviations that could confound the interpretation of analyses conducted on the FAS. Major protocol deviations will be determined according to the pre-defined protocol deviation criteria before treatment unblinding (e.g. non-compliance for a large proportion of the time in study). For analyses performed on the PPS, only efficacy data assessed during the on treatment period (as defined in [Section 2.1.1](#)) will be included.

The PPS will be used for the supportive analyses of the primary efficacy variable and selected key secondary variables.

Safety set (SAF): The SAF set includes all patients who received at least one dose of study medication. Patients will be analyzed according to the actual treatment received. If patients received both investigational drug and active comparator accidentally during the study, they

will be analyzed according to the treatment to which they were exposed longer in duration. The SAF will be used for all safety analyses.

2.2.1 Subgroup of interest

Only protocol specified subgroup analyses will be covered in the CSR. Subgroup analyses on the pooled study data for submission purpose are out of the scope of this SAP but will be specified in the relevant submission plan document (e.g., Clinical Summary Preparation Document (CSPD)). As subgroup analyses do not control for either type I or type II error, they should be considered as hypothesis generating in nature with the purpose of examining potential inconsistencies of a treatment among the many subgroups being examined. All confidence intervals and p-values for subgroup analysis will be presented without multiplicity adjustments.

Subgroups for efficacy analyses:

- NfL level (high:>median, low:<=median), where the median is defined based on all patients in the FAS of the combined data from both ASCLEPIOS studies.
- NfL levels (<Q1; >=Q1 but <Q2; >=Q2 but < Q3; >=Q3; where Q1, Q2 and Q3 are first, second and third quartiles of baseline neurofilament levels in all patients from studies G2301 and G2302 combined)
- Vitamin D levels (<Q1; >=Q1 but <Q2; >=Q2 but < Q3; >=Q3; where Q1, Q2 and Q3 are first, second and third quartiles of baseline vitamin D levels in all patients from studies G2301 and G2302 combined)
- Newly diagnosed (within 3 years prior to the screening visit) and treatment-naïve (no prior MS DMT) patients

These subgroups will be used for selected exploratory analyses as described in [Section 2.12](#).

Subgroups for safety analyses:

- Age at baseline (<18, 18-30, 31-40, 41-55, >55)
- Gender (male, female)
- Gender x Age: 10 subgroups defined by age and gender: female & age <18; female & age of 18-30; female & age of 31-40; female & age of 41-55; female & age >55; male & <18; male & age of 18-30; male & age of 31-40; male & age of 41-55; male & age >55;
- Gender x body weight (by quartile): 8 subgroups defined by gender and baseline body weight: female & weight <Q1; female & weight >=Q1 but <Q2; female & weight >=Q2 but < Q3; female & weight >=Q3; male & weight <Q1; male & weight >=Q1 but <Q2; male & weight >=Q2 but < Q3; male & weight >=Q3; where Q1, Q2 and Q3 are first, second and third quartiles of baseline weight in all patients from studies G2301 and G2302 combined
- Race (White, Asian, Black or African American, Other)
 - White: those who selected “Caucasian” as race on demography CRF
 - Asian: those who selected “Asian” as race on demography CRF
 - Black or African American: those who selected “Black” as race on demography CRF

- Other: those who selected “Native American” or “Pacific Islander” or “Unknown” or “Other” as race on demography CRF
- *Patients who accidentally received both investigational drug and active comparator during the study
- **Patients in SAF who had data reported after date of last administration of study drug
- **Patients in SAF who had at least one eCSSRS performed after the date of last administration of study drug
- **Patients in SAF who had B-cell count data after the date of last administration of study drug
- **Patients in SAF who had teriflunomide data

*This subgroup will be used for exploratory analysis described in [Section 2.8.1](#). **These subgroups will be used for corresponding safety follow up data analysis described in [Section 2.8.7](#). Rest of the subgroups will be used for patient-year summaries described in [Section 2.4.1](#).

2.3 Patient disposition, demographics and other baseline characteristics

2.3.1 Patient disposition

The number and percentage of patients who were screened but did not continue into the treatment period will be presented, along with the reason for discontinuation. Data collected on the screening phase disposition CRF page will be used to summarize this information. The summary will be on the SCR set.

The number and percentage of patients who completed the study on treatment or prematurely discontinued study drug will be presented, along with the primary reason for discontinuation. Data collected on the end of study treatment CRF page will be used to summarize this information. The summary will be on the FAS.

The number and percentage of patients who completed the study (i.e., treatment epoch) or prematurely discontinued study prior to the end of the treatment epoch will be presented, along with the primary reason for discontinuation. Data collected on the study phase completion CRF page will be used to summarize this information. The summary will be on the FAS.

Time to study drug discontinuations and time to study discontinuations by treatment group will be presented using Kaplan-Meier estimates in survival curves and in summary tables, along with the p-value from the log-rank test. Time to study drug discontinuation (in days) will be derived as [last dose date – first dose date + 1]. Time to study discontinuation (in days) will be derived as [date of discontinuation/study phase completion” for the treatment epoch – first dose date + 1]. The event flag for analysis of time to study drug discontinuations is set to 1 for patients who answered “No” to question “did the subject complete study treatment” as recorded on End of Study Treatment CRF page or 0 otherwise. The event flag for analysis of time to study discontinuations is set to 1 for patients whose “subject status” is not “completed” as recorded on Study Phase Completion CRF page or 0 otherwise. These analyses will be on the FAS.

The number and percentage of patients in each analysis set will be presented by treatment group. Protocol deviations will be summarized by deviation categories and treatment for the FAS. In addition, protocol deviations that led to exclusion from the analysis set will be summarized by deviation category, deviation terms and treatment groups for the FAS.

Patients exclusion from PPS will be listed for all patients with reasons for exclusion (i.e. including both protocol and non-protocol deviations).

2.3.2 Background and demographic characteristics

Background characteristics include recipient demographic characteristics (gender, race and ethnicity collected on the Demography CRF), age, height, body weight, BMI and employment status at baseline.

Age will be calculated from date of first administration of study drug and date of birth. Derived baseline height, body weight and BMI will be presented. These variables will be summarized by treatment group for the FAS using frequency distributions (for categorical variables) and descriptive statistics of mean, standard deviation, minimum, median and maximum (for continuous variables).

Demography will be presented by study but also side-by-side for the two studies in the combined report to evaluate poolability of the two ASCLEPIOS trials.

2.3.3 MS baseline disease characteristics

MS baseline characteristics, MS disease history and MS medication history will be summarized by treatment group for the FAS in the individual study reports but also side-by-side for the two studies in the combined report to evaluate poolability of the two ASCLEPIOS trials.

MS baseline characteristics include baseline EDSS, 9HPT, T25FW, SDMT, and key MRI parameters (e.g., number of Gd-enhancing T1 lesions, T2 lesion volume, and normalized brain volume).

MS disease history includes duration of MS since diagnosis (years), duration of MS since first symptom (years), number of relapses in the last 12 months prior to screening, number of relapses in the 12 to 24 months prior to screening, type of MS at study entry (i.e., RRMS or SPMS), time since onset of SPMS, and time since onset of most recent relapse (months) prior to screening.

Duration of MS since diagnosis (years) will be derived $[(\text{first dose date} - \text{MS diagnosis start date} + 1)/365.25]$; duration of MS since first symptom (years) will be derived as $[(\text{first dose date} - \text{first MS symptom date} + 1)/365.25]$; time since onset of SPMS (years) will be derived as $[(\text{first dose date} - \text{conversion to SPMS date} + 1)/365.25]$; and time since onset of most recent relapse (months) will be derived as $[(\text{first dose date} - \text{most recent relapse onset date} + 1)/(365.25/12)]$. In these calculations, partial dates if any will be imputed according to the rules specified in [Section 5.1.3.3](#).

MS medication history of previous disease-modifying drugs (coded by WHO drug dictionary) will be summarized by preferred term (PT) and treatment group. The number and proportion of treatment-naïve patients (i.e., patients who have not been treated with any disease-modifying drug before study enrolment) will also be presented.

2.3.4 Medical history

Medical history will be summarized by treatment group for the FAS. Any condition entered on the Medical History (MH) CRF will be coded using the MedDRA dictionary. The medical history will be summarized by primary system organ class (SOC), preferred term (PT) and treatment group.

The MH conditions captured on the eCRF “Protocol solicited medical history or medical history possibly contributing to liver dysfunction” will be tabulated in the regular MH table for level 2 drugs (because the solicited events are captured for all patients) and shown and flagged in the regular MH listing. There is no separate deliverable required.

2.3.5 Smoking history and alcohol history

Data collected on smoking history and alcohol history CRF pages will be listed as appropriate.

2.4 Treatments (study treatment, rescue medication, concomitant therapies, compliance)

2.4.1 Exposure to study treatment / compliance / time at risk

Duration of exposure to study drug will be derived as follows:

- For patients whose actual treatment ([Section 2.2](#) Safety set) is teriflunomide, duration of exposure will be calculated as (last dose date – first dose date +1 - Σ [number of days with temporary study drug interruption]), which is the number of days between the first and the last day of study drug administration, excluding the number of days with temporary study drug interruption (as patients are scheduled to take the oral study medication once daily).
- For patients whose actual treatment is ofatumumab, duration of exposure will be calculated as (last injection date – first injection date + 31 – Σ [(j+1)th injection date – jth injection date -31]), where j and j+1 refer to consecutive injections with injection dates more than 31 days apart (as patients are scheduled to take the subcutaneous injections every 28 +/- 3 days).

Duration of exposure to study drug will be summarized descriptively on SAF set by treatment group and duration category (i.e., ≥ 1 week, ≥ 2 weeks, ≥ 3 weeks, ≥ 4 weeks, ≥ 8 weeks, ≥ 12 weeks, ≥ 24 weeks, ≥ 36 weeks, ≥ 48 weeks, ≥ 60 weeks, ≥ 72 weeks, ≥ 84 weeks, ≥ 96 weeks, ≥ 108 weeks, ≥ 120 weeks, ≥ 132 weeks, ≥ 144 weeks, ≥ 156 weeks, ≥ 168 weeks). Descriptive statistics of duration in days will also be provided by treatment group.

For each treatment group, the number of patient-years is calculated as (the sum of the number of days of exposure for all patients in the group)/365.25 and will be summarized by age and gender, by gender and weight, as well as by race. Cutoffs for age subgroups and weight subgroups are defined in [Section 2.2.1](#).

Time at risk is the censoring time used for estimating exposure adjusted incidence rate of SAEs or AEs in patients who did not experience the event of interest. For patients who have experienced the event of interest, the actual date of the SAE, or AE onset will be used. Details

about the calculation of exposure adjusted incidence rate of adverse events are described in [Section 5.7.2](#). Time at risk also corresponds to the time period used for adverse event reporting.

- **Time at risk for AE** is defined as the number of days spent in the study, from first to last administration of study drug, plus the safety data cut-off of 100 days. Time at risk for AE will be used for tables reporting AEs (including both SAE and non-SAE). If the corresponding last day of time at risk for AE is after the analysis cut-off date, then it will be truncated by the analysis cut-off date as defined in [Section 2.1](#).
- **Time at risk for SAE** is defined as the number of days spent in the study from the day of first administration of study drug to the end of study date (including safety follow up epoch). Time at risk for SAE will be used only for tables reporting SAEs. If a patient is still in safety follow up epoch at the time of reporting, time at risk for SAE is the number of days from the day of first administration of study drug to the analysis cut-off date as defined in [Section 2.1](#).

Time at risk for AE and time at risk for SAE will be summarized in a similar way to duration of exposure to study drug.

Compliance to the study drug administration schedule will be calculated as duration of exposure to study drug in (days)/duration of on-treatment period (as defined in [Section 2.1.1](#)) in (days) $\times 100\%$. This rule means that compliance will be measured during the time interval the patient took study medication: premature discontinuation from study drug will not be considered non-compliance. Compliance to study drug administration will be summarized descriptively on SAF by treatment group. In addition, compliance will be summarized with cumulative number and percentage of patients in each compliance category (*i.e.*, $\geq 20\%$, $\geq 30\%$, $\geq 40\%$, $\geq 50\%$, $\geq 60\%$, $\geq 70\%$, $\geq 80\%$, $\geq 90\%$, $\geq 95\%$, $\geq 98\%$, $=100\%$).

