3.3 Rationale for dose/regimen, route of administration and duration of treatment

The dose regimen for ofatumumab for this study is a *loading dose regimen* of 20 mg at Day 1, Day 7 and Day 14, followed by a monthly *maintenance dose regimen* of 20 mg administered every 4 weeks starting at week 4. The dose selection relies on the clinical hypothesis that the depletion of B-cells in lymphatic tissues is key for efficacy (as measured by MRI and relapses), and that the depletion of brain parenchymal and meningeal B-cells may be an additional factor for the mode of action; blood B-cell count is an imperfect, epiphenomenal measure of tissue status. This hypothesis suggests that in order to attain the desired efficacy, 2 conditions should be met:

- A loading regimen with high enough initial PK for lymphatic depletion, and

- A continued maintenance dose that would keep B-cell depletion levels below desired threshold.

The Phase 2 study of ofatumumab sc in relapsing MS patients (Study OMS112831) provided important information regarding the relationship between peripheral B-cell depletion and efficacy as measured by MRI Gd-enhancing brain lesions. Clear dose-response relationship was detected using a quasi-Poisson regression model that related new Gd-enhancing lesion volumes, baseline lesion number and treatment group. The dose-response was fully explained by the extent of the CD19⁺ cell count drop. The model indicates that lower CD19⁺ cells levels lead to better control of lesion volumes and, subsequently, high level of depletion of CD19⁺ cells (e.g. ≤ 8 cells/ μ L) should be maintained throughout the treatment course in order to ensure desired efficacy.

Pharmacokinetic/pharmacodynamic (PK/PD) modeling on the Phase 2 data of study OMS112831 suggested that a single dose of ofatumumab 20 mg sc is insufficient to reduce B-cell levels to ≤ 8 cells/ μ L. A loading regimen of 3 separate 20 mg (at weeks 0, 1 and 2) was required to attain target depletion (≤ 8 cells/ μ L) in $> 95\%$ of patients based on modeling, and is extrapolated to be more effective than a single 60 mg load. In study OMS112831, patients dosed with 60 mg q4 weeks showed no signs of B-cell repletion during the inter-dosing interval. Based on PK/PD modeling, 20 mg ofatumumab appears to be sufficient to either maintain or to further deplete B-cells in $> 95\%$ of patients who have previously depleted, even in patients with high repletion rates.

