5.2 Treatment arms

The study includes 2 treatment arms:

- Ofatumumab arm: ofatumumab 20 mg sc injections on Day 1, 7, 14, Week 4 (Study Month 1) and every 4 weeks thereafter + teriflunomide-matching placebo capsule orally once daily.
- Teriflunomide arm: teriflunomide 14 mg capsule orally once daily + ofatumumab-matching placebo injections on Day 1, 7, 14, Week 4 (Study Month 1) and every 4 weeks thereafter.

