Baseline	Baseline is the last assessment obtained prior to the first administration of study drug. No visit windows will be needed for the identification of baseline assessment. For pulse and blood pressure vital sign values, the baseline is the average of the non-missing values of the 3 measurements taken on the last visit prior to the first administration of study drug. The pre-injection assessment values on Day 1 vital sign CRF page will not be used for baseline derivations.
On-treatment period	For patients randomized to receive ofatumumab, on-treatment period includes days from the first injection date until 30 days after the last injection date; for patients randomized to receive teriflunomide, on-treatment period includes days from the first dose date until the last dose date. This definition considers patients on ofatumumab are scheduled to inject every 28 +/- 3 days. The on-treatment definition applies to efficacy analyses only. For calculation of compliance to study drug administration, similar definition of on-treatment period except based on actual treatment assignment will be used.
Safety cutoff (off-treatment)	Safety cutoff: Unless explicitly otherwise stated (e.g. SAEs and deaths), data up to and including the safety cutoff of 100 days after permanent study drug discontinuation will be

	included in the analysis and data beyond this time point for a given patient will be excluded from the safety analysis. The safety cutoff of 100 days (5x20 days) takes the long half-life of both investigational and comparator-drug into account. The safety cutoff applies to safety analyses only.
Nominal visits	Nominal visits are defined as all scheduled visits as per the clinical study protocol including the EOS and EOT visits. The definition of nominal visit excludes unscheduled visits. Only vital signs data collected on Day 1, Day 7, Day 14 and Month 1 protocol scheduled visit and ECG data collected on EOT and EOS visits will be summarized by nominal visit.
End of Study (EOS)	EOS, used in the context of individual patients, refers to EOS visit. EOS, used in the context of the entire study, refers to completion of treatment epoch for all patients.
End of Treatment (EOT)	EOT refers to EOT visit. Only patients who prematurely discontinue study drug but agree to continue to follow the schedule of assessments in the treatment epoch will have EOT visit.

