COMD03	Any other immunomodulatory or disease- modifying MS treatment, including but not limited to, fingolimod, interferon beta, glatiramer acetate, dimethyl fumarate or systemic corticosteroids (except when given for MS Relapse treatment) while taking double-blind treatment	Excluded from PPS
COMD04	Leflunomide while taking double-blind treatment	Excluded from PPS
COMD06	Daclizumab while taking double-blind treatment	Excluded from PPS
OTH01	EDSS rater acted as a treating physician or treating physician acted as EDSS rater	Excluded from PPS
OTH02	Not following per protocol blinding procedures such that the integrity of the study is compromised	Excluded from PPS

Table 5-8 Patient Classification

Analysis Set	PD ID that cause patients to be excluded	Non-PD criteria that cause patients to be excluded
SCR	NA	NA
FAS	INCL01	Not assigned a valid randomization number Mis-randomized patients who didn't take study drug
PPS	As listed in Table 5.7	Not in FAS;

Analysis Set	PD ID that cause patients to be excluded	Non-PD criteria that cause patients to be excluded
		Compliance to study drug administration < 80%
		EDSS baseline value >=7.0
SAF	INCL01	No double-blind study drug taken

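### The SAP's ofatumumab compliance formula cannot register a missed Day 7 or Day 14 loading injection, so a patient who misses both is reported as 100% compliant

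*SAP*

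**What the plan says.** Protocol 5.2 gives the active regimen as "ofatumumab 20 mg sc injections on Day 1, 7, 14, Week 4 (Study Month 1) and every 4 weeks thereafter".

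SAP 2.4.1 takes ofatumumab exposure as last injection date minus first injection date plus 31, less the excess over 31 days of each long gap, "where j and j+1 refer to consecutive injections with injection dates more than 31 days apart". The stated reason for the 31 days is "as patients are scheduled to take the subcutaneous injections every 28 +/- 3 days". That is the maintenance interval. The section has no separate allowance for the loading injections.

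The ratio is defined as follows: "Compliance to the study drug administration schedule will be calculated as duration of exposure to study drug in (days)/duration of on-treatment period". For ofatumumab the "on-treatment period includes days from the first injection date until 30 days after the last injection date" (SAP 2.1.1, Table 2-1), and the same section adds: "For calculation of compliance to study drug administration, similar definition of on-treatment period except based on actual treatment assignment will be used".

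The result is used in two places. SAP 2.4.1 tabulates it on the safety set by cumulative category, the highest being exactly 100%. SAP 5.6, Table 5-8, excludes patients from the per-protocol set (PPS) for "Compliance to study drug administration < 80" per cent. As printed, the treatment-related deviation codes in Table 5-7 cover incorrect drug and damaged or expired drug. None covers a missed injection.

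**The concern.** The measure is presented as adherence to the dosing schedule, but it checks only the maintenance part of that schedule. The scheduled gaps between the first four injections are 6, 7 and 14 days. Missing one or both of the middle injections leaves every gap well under 31 days.

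The loading phase is not incidental in this protocol. Section 3.3 reports that modelling of Phase 2 data "suggested that a single dose of ofatumumab 20 mg sc is insufficient to reduce B-cell levels" to the target, and it rests the choice of three weekly doses on that modelling. A compliance table that cannot show whether those doses were taken gives the reader wrong figures on a feature the protocol treats as important.

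The two arms are also measured differently. For teriflunomide, every day of temporary interruption is deducted. For ofatumumab, two missed loading injections cost nothing.

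**Working it through.** The documents give no compliance figure to reproduce, so the formula was applied to hypothetical injection histories.

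**Inputs.** Injection days 1, 7, 14, 28, then every 28 days (Protocol 3.1 and 5.2). Exposure formula and ratio (SAP 2.4.1). On-treatment period (SAP 2.1.1). Cut-off of 80% (SAP Table 5-8). Planning follow-up of 1.5 years (Protocol 9.8.1).

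**Formula.**
- Exposure = last − first + 31 − Σ(gap − 31), summed over gaps above 31 days.
- On-treatment days = (last + 30) − first + 1 = last − first + 31.

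The two are identical unless some gap exceeds 31 days, so compliance falls below 100% only in that case. A fully adherent patient scores 100%, as intended.

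**Gaps when loading injections are missed.**
- Day 7 missed: 14 − 1 = 13 days.
- Day 14 missed: 28 − 7 = 21 days.
- Both missed: 28 − 1 = 27 days.
- Both missed, Month 1 given 3 days late: 31 − 1 = 30 days.
- As above, but with Week 4 counted as Day 29: 32 − 1 = 31 days, still not more than 31.

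The deduction is zero in every case.

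**Both loading injections missed, later injections on time.**

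| Follow-up to | Last injection | SAP formula | Injections received / scheduled |
|---|---|---|---|
| Day 168 | Day 168 | 198/198 = 100% | 7/9 = 77.8% |
| Day 336 | Day 336 | 366/366 = 100% | 13/15 = 86.7% |
| Day 548 (1.5 years) | Day 532 | 562/562 = 100% | 20/22 = 90.9% |
| Day 840 | Day 840 | 870/870 = 100% | 31/33 = 93.9% |

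**Contrast.** Missing only the Month 1 injection gives a gap of 56 − 14 = 42 days and a deduction of 11. Compliance to 1.5 years is then 551/562 = 98.0%. One missed injection at Month 1 lowers the score, while two missed a fortnight earlier do not.

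**Effect on the 80% rule.** By count, a patient who misses both loading injections scores (N − 2)/N, where N is the number scheduled. This is below 80% only for N of 9 or fewer, that is, with the last injection at Day 168 or earlier. At N = 10 (Day 196) it is 8/10 = 80.0% and the patient stays in.

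Keeping a day-based measure but allowing 7 to 9 days after Day 1 (an assumed range) deducts 27 − 9 = 18 to 27 − 7 = 20 days. At 1.5 years this gives 542/562 = 96.4% to 544/562 = 96.8%, also well above the cut-off.

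**The case against.** A reader might infer that the formula is what keeps under-loaded patients in the PPS, and that the per-protocol analyses of relapse rate and disability worsening are compromised as a result. The documents do not support that. A count-based measure still gives 90.9% at 1.5 years, so retention comes mainly from a cut-off applied over the whole treatment period. That cut-off fits the stated idea of a major deviation in Protocol 9.1 and SAP 2.2, where the example is non-compliance over a large part of the time in study. The PPS is also supportive only; the primary and confirmatory analyses use the full analysis set. If under-loaded patients do respond less well, keeping them would tend to work against ofatumumab.

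A reader might also infer that a missed loading injection should be a PPS exclusion in its own right. That would sit badly with the 80% rule. Four isolated missed maintenance injections cost 4 × (56 − 31) = 100 days, and 462/562 = 82.2% keeps that patient in. Excluding someone for 1 missed injection of 22 (21/22 = 95.5%) would be stricter for a smaller lapse. It would also either apply to one arm only or remove teriflunomide patients for missing a placebo injection.

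A third example is a patient who takes Day 1 and Day 28 and then stops. The formula gives 58/58 = 100%, although only 2 of 4 scheduled injections were received. The stopping itself is not the defect, because SAP 2.4.1 says explicitly that premature discontinuation is not non-compliance.

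Finally, injections on Days 1, 7, 14 and 28 are given or supervised at the site, and missed doses are recorded and listed. The lapse may be rare and would remain visible in listings. All of this limits the consequence. None of it makes 100% the right value for a patient who missed two scheduled injections.

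**Conclusion.** The point holds as a defect in a prespecified adherence measure. A missed Day 7 injection, Day 14 injection, or both, followed by an on-time Month 1 injection, is never penalised. A patient who misses both is reported as fully compliant when the proportion received is 77.8% to 93.9%, for last injections from Day 168 to Day 840. This assumes that later injections are on time.

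The safety-set compliance table is directly wrong for these patients. PPS membership would change mainly for those with short treatment: a patient missing both loading injections falls below 80% only if the last injection is at Day 168 or earlier. No primary or confirmatory test is affected. The documents do not say how many patients are involved. They also give no B-cell depletion estimate for a patient who misses Days 7 and 14 but continues monthly dosing, so no loss of efficacy can be quantified.

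**What to change.** In SAP 2.4.1, for patients whose actual treatment is ofatumumab, define compliance as active injections received divided by injections scheduled (Days 1, 7, 14, 28, then every 28 days) up to the last injection received. State that the denominator runs through the scheduled injection to which the last one is assigned, so that an injection given early within its window does not push the ratio above 100%. Stopping at the last injection keeps the SAP's rule that discontinuation is not non-compliance.

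Use this value in the compliance table and in the existing 80% rule of Table 5-8. Leave the exposure duration used for patient-years and the teriflunomide measure unchanged. Add no separate exclusion for a missed loading injection. If the question matters to the team, a labelled sensitivity analysis is enough.

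The cost is one derived variable and a few lines of SAP text, since injection dates are already collected on the Dosage Administration Record. One property changes: an injection given late but not skipped counts as received, so lateness would show only in listings. PPS criteria are to be fixed before unblinding, and this SAP already carries an addendum dated after database lock. If treatment codes are open, present the count-based table as a correction and any per-protocol re-analysis as a labelled sensitivity analysis.
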